A food effect study involving administration of DFX as Jadenu to healthy subjects under fasting conditions and with a low-fat (fat content <7% of total calories) or high-fat (fat content >50% of total calories) meal indicated that the AUC and C_{max} were slightly decreased after a low-fat meal (by 11% and 16%, respectively). After a high-fat meal, AUC and C_{max} were increased by 18% and 29%, respectively. The increases in C_{max} due to the change in formulation and due to the effect of a high-fat meal may be additive and therefore, it is recommended that DFX as Jadenu should be taken on an empty stomach or with a light meal (contains less than 7% fat content and approximately 250 calories) [5].

To date, two Phase 1 studies with DST-0509 have been performed. A non-US Phase 1 pilot PK study (OPA-P8-807; Study 101) has been completed in Canada. The study was titled, "Single Dose Crossover Comparative Oral Bioavailability Under Fasting Conditions and Food Effect Pilot Study of Two Deferasirox Formulations and Jadenu 360 mg Tablets in Healthy Male and Female Volunteers". This Phase 1 study was a first-in-human, single center, single dose, crossover oral bioavailability pilot study. The purpose of the Phase 1 study was to provide PK data for two oral dose formulations of DST-0509 following oral administration to healthy subjects in fed and fasted states, compared with Jadenu. The results showed that as hypothesized, the Test (DST-0509) and Reference (Jadenu) formulations were not bioequivalent, with higher bioavailability on a molar basis for the DST-0509 test formulations.

The second Phase 1 study (DIS-P4-592; Study 102) has been completed in Canada. The study was titled "Single Dose Crossover Oral Bioavailability Study of a New Deferasirox Formulation Compared to Exjade Dispersible Tablets and Jadenu Tablets in Healthy Male and Female Volunteers." This was a single center, single dose, randomized, 3-period, 3-sequence crossover, oral bioavailability study of DST-0509 compared with Exjade and Jadenu in fasted healthy volunteers. The results showed less variability in C_{max} and AUC with DST-0509 versus Exjade,

and meaningfully enhanced absorption of DST-0509 versus Exjade and Jadenu. The enhanced bioavailability and reduced PK variability observed in Study 102 on an equivalent molar basis are expected to translate into less variability in response and improved efficacy in patients who do not respond well to currently available DFX products.

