6.3.2 Visit 4 (Day 7 ±1 day)

Procedures as identified in Table 6-1.

- Adverse Events
- Concomitant Medications
- Review GI AESI diary
- Review Bristol Stool Chart diary
- Treatment Compliance
- Pharmacokinetic sampling at predose (-0.5 hour) and 1, 2, 4, and 8 hours postdose
- Patients are instructed not to take study medication on the morning before they arrive for their next visit

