7.11.3 Collection, Shipment, and Retention of Laboratory Samples

All safety laboratory analyses will be performed by either a central or local laboratory. If a central laboratory is utilized, central laboratory will provide all collection materials and instructions for sample collection, packaging, and shipment. Samples for chemistry, hematology (CBC) and urinalysis will be collected at Screening and on Days 1, 14, 28, 36, 49 and 63. Samples for serum CRP will be collected at Screening and on Days 1, 28, 36, and 63.

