14 CLINICAL STUDIES

16 HOW SUPPLIED/STORAGE AND HANDLING

17 PATIENT COUNSELING INFORMATION

* Sections or subsections omitted from the full prescribing information are not listed.

FULL PRESCRIBING INFORMATION

WARNING: RENAL FAILURE, HEPATIC FAILURE, AND GASTROINTESTINAL HEMORRHAGE

Renal Failure

- Exjade can cause acute renal failure and death, particularly in patients with comorbidities and those who are in the advanced stages of their hematologic disorders.
- Measure serum creatinine and determine creatinine clearance in duplicate prior to initiation of therapy and monitor renal function at least monthly thereafter. For patients with baseline renal impairment or increased risk of acute renal failure, monitor creatinine weekly for the first month, then at least monthly. Consider dose reduction, interruption, or discontinuation based on increases in serum creatinine [see *Dosage and Administration* (2.4, 2.5), *Warnings and Precautions* (5.1)].

Hepatic Failure

- Exjade can cause hepatic injury including hepatic failure and death.
- Measure serum transaminases and bilirubin in all patients prior to initiating treatment, every 2 weeks during the first month, and at least monthly thereafter.
- Avoid use of Exjade in patients with severe (Child-Pugh C) hepatic impairment and reduce the dose in patients with moderate (Child Pugh B) hepatic impairment [see *Dosage and Administration* (2.4), *Warnings and Precautions* (5.2)].

Gastrointestinal Hemorrhage

- Exjade can cause gastrointestinal (GI) hemorrhages, which may be fatal, especially in elderly patients who have advanced hematologic malignancies and/or low platelet counts.
- Monitor patients and discontinue Exjade for suspected GI ulceration or hemorrhage [see *Warnings and Precautions* (5.3)].

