Table 1 displays adverse reactions occurring in >5% of Exjade-treated beta-thalassemia patients (Study 1), sickle cell disease patients (Study 3), and patients with MDS (MDS pool). Abdominal pain, nausea, vomiting, diarrhea, skin rashes, and increases in serum creatinine were the most frequent adverse reactions reported with a suspected relationship to Exjade. Gastrointestinal symptoms, increases in serum creatinine, and skin rash were dose related.

Table 1. Adverse Reactions* Occurring in >5% of Exjade-treated Patients in Study 1, Study 3, and MDS Pool

	Study 1 (Beta-thalassemia)		Study 3 (Sickle Cell Disease)		MDS Pool
	EXJADE N=296 n (%)	Deferoxamine N=290 n (%)	EXJADE N=132 n (%)	Deferoxamine N=63 n (%)	EXJADE N=627 n (%)
Preferred Term					
Abdominal Pain**	63 (21)	41 (14)	37 (28)	9 (14)	145 (23)
Diarrhea	35 (12)	21 (7)	26 (20)	3 (5)	297 (47)
Creatinine Increased***	33 (11)	0 (0)	9 (7)	0	89 (14)
Nausea	31 (11)	14 (5)	30 (23)	7 (11)	161 (26)
Vomiting	30 (10)	28 (10)	28 (21)	10 (16)	83 (13)
Rash	25 (8)	9 (3)	14 (11)	3 (5)	83 (13)

*Adverse reaction frequencies are based on adverse events reported regardless of relationship to study drug.

**Includes 'abdominal pain', 'abdominal pain lower', and 'abdominal pain upper' which were reported as adverse events.

***Includes 'blood creatinine increased' and 'blood creatinine abnormal' which were reported as adverse events. Also see Table 2

In Study 1, a total of 113 (38%) patients treated with Exjade had increases in serum creatinine >33% above baseline on 2 separate occasions (Table 2) and 25 (8%) patients required dose reductions. Increases in serum creatinine appeared to be dose related [see *Warnings and Precautions* (5.1)]. In this study, 17 (6%) patients treated with Exjade developed elevations in SGPT/ALT levels >5 times the upper limit of normal at 2 consecutive visits. Of these, 2 patients had liver biopsy proven drug-induced hepatitis and both discontinued Exjade therapy [see *Warnings and Precautions* (5.2)]. An additional 2 patients, who did not have elevations in SGPT/ALT >5 times the upper limit of normal, discontinued Exjade because of increased SGPT/ALT. Increases in transaminases did not appear to be dose related. Adverse reactions that led to discontinuations included

abnormal liver function tests (2 patients) and drug-induced hepatitis (2 patients), skin rash, glycosuria/proteinuria, Henoch Schönlein purpura, hyperactivity/insomnia, drug fever, and cataract (1 patient each).

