2.5 Dose Modifications for Increases in Serum Creatinine

For serum creatinine increases while receiving JADENU [see *Warnings and Precautions (5.1)*] modify the dose as follows:

Transfusional Iron Overload

Adults and Adolescents (ages 16 years and older):

- If the serum creatinine increases by 33% or more above the average baseline measurement, repeat the serum creatinine within 1 week, and if still elevated by 33% or more, reduce the dose by 7 mg per kg.

Pediatric Patients (ages 2 to 15 years):

- Reduce the dose by 7 mg per kg if serum creatinine increases to greater than 33% above the average baseline measurement and greater than the age appropriate ULN.

All Patients (regardless of age):

- Discontinue therapy for serum creatinine greater than 2 times the age-appropriate ULN or for creatinine clearance less than 40 mL/min. [see *Contraindications (4)*]

Non-Transfusion-Dependent Thalassemia Syndromes

Adults and Adolescents (ages 16 years and older):

- If the serum creatinine increases by 33% or more above the average baseline measurement, repeat the serum creatinine within 1 week, and if still elevated by 33% or more, interrupt therapy if the dose is 3.5 mg per kg, or reduce by 50% if the dose is 7 or 14 mg per kg.

Pediatric Patients (ages 10 to 15 years):

- Reduce the dose by 3.5 mg per kg if serum creatinine increases to greater than 33% above the average baseline measurement and greater than the age appropriate ULN.

All Patients (regardless of age):

- Discontinue therapy for serum creatinine greater than 2 times the age-appropriate ULN or for creatinine clearance less than 40 mL/min [see *Contraindications (4)*].

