5 WARNINGS AND PRECAUTIONS

5.1 Renal Toxicity, Renal Failure, and Proteinuria

JADENU can cause acute renal failure, fatal in some patients and requiring dialysis in others. Postmarketing experience showed that most fatalities occurred in patients with multiple comorbidities and who were in advanced stages of their hematological disorders. In the clinical trials, deferasirox-treated patients experienced dose-dependent increases in serum creatinine. In patients with transfusional iron overload, these increases in creatinine occurred at a greater frequency compared to deferoxamine-treated patients (38% versus 14%, respectively, in Study 1 and 36% versus 22%, respectively, in Study 3) [see *Adverse Reactions (6.1, 6.2)*].

Measure serum creatinine in duplicate (due to variations in measurements) and determine the CrCl (estimated by the Cockcroft-Gault method) before initiating therapy in all patients in order to establish a reliable pretreatment baseline. Monitor serum creatinine weekly during the first month after initiation or modification of therapy and at least monthly thereafter. Monitor serum creatinine and/or CrCl more frequently if creatinine levels are increasing. Dose reduction, interruption, or discontinuation based on increases in serum creatinine may be necessary [see *Dosage and Administration (2.5)*].

JADENU is contraindicated in patients with CrCl less than 40 mL/minute or serum creatinine greater than 2 times the age appropriate ULN.

Renal tubular damage, including Fanconi's Syndrome, has been reported in patients treated with deferasirox, most commonly in children and adolescents with beta-thalassemia and serum ferritin levels <1500 mcg/L.

Intermittent proteinuria (urine protein/creatinine ratio >0.6 mg/mg) occurred in 18.6% of deferasirox-treated patients compared to 7.2% of deferoxamine-treated patients in Study 1. In clinical trials in patients with transfusional iron overload, deferasirox was temporarily withheld until the urine protein/creatinine ratio fell below 0.6 mg/mg. Monthly monitoring for proteinuria is recommended. The mechanism and clinical significance of the proteinuria are uncertain [see *Adverse Reactions (6.1)*].

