5.2 Hepatic Toxicity and Failure

Deferasirox can cause hepatic injury, fatal in some patients. In Study 1, 4 patients (1.3%) discontinued deferasirox because of hepatic toxicity (drug-induced hepatitis in 2 patients and increased serum transaminases in 2 additional patients). Hepatic toxicity appears to be more common in patients greater than 55 years of age. Hepatic failure was more common in patients with significant comorbidities, including liver cirrhosis and multiorgan failure [see *Adverse Reactions (6.1)*].

Measure transaminases (AST and ALT) and bilirubin in all patients before the initiation of treatment and every 2 weeks during the first month and at least monthly thereafter. Consider dose modifications or interruption of treatment for severe or persistent elevations.

Avoid the use of JADENU in patients with severe (Child-Pugh C) hepatic impairment. Reduce the starting dose in patients with moderate (Child-Pugh B) hepatic impairment [see *Dosage and Administration* (2.4), *Use in Specific Populations* (8.7)]. Patients with mild (Child-Pugh A) or moderate (Child-Pugh B) hepatic impairment may be at higher risk for hepatic toxicity.

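### Low-severity improvement: adding serum creatinine at the existing Day 7 and Day 42 visits would bring the first scheduled on-drug value forward from 13 days to 6 in each period

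*Protocol*

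**What the plan says.** Protocol section 7.11.3 fixes the safety laboratory days: "Samples for chemistry, hematology (CBC) and urinalysis will be collected at Screening and on Days 1, 14, 28, 36, 49 and 63". Section 7.11.1 places serum creatinine in the chemistry panel. Table 6-1 and the visit lists in sections 6.3 and 6.4 agree with this. Urine protein and creatinine follow the same on-study days, so they do not fill the interval.

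Dosing starts on Day 1 in Period 1 (section 5.4) and at Visit 7, Day 36, in Period 2 (section 6.4.1). Between the first dose and the first on-drug chemistry of each period there is one clinic visit: Visit 4 (Day 7, section 6.3.2) or Visit 8 (Day 42, section 6.4.2). Each lists "Pharmacokinetic sampling at predose (-0.5 hour) and 1, 2, 4, and 8 hours postdose", which is five samples, together with adverse event review, but no chemistry.

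The appended labels (Appendices A and B) bear on this in four places:

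- Section 5.1, renal: "Monitor serum creatinine weekly during the first month after initiation or modification of therapy and at least monthly thereafter".
- Section 5.2, hepatic: "Measure transaminases (AST and ALT) and bilirubin in all patients before the initiation of treatment and every 2 weeks during the first month".
- Boxed warning: renal monitoring at least monthly in general, and "For patients with baseline renal impairment or increased risk of acute renal failure, monitor creatinine weekly for the first month, then at least monthly".
- Section 2.5, adults: "If the serum creatinine increases by 33% or more above the average baseline measurement, repeat the serum creatinine within 1 week".

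DST-0509 is dosed milligram for milligram against Jadenu, or at 28/40 of the Exjade dose (section 5.4).

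**The concern.** Safety is a primary endpoint, and renal toxicity is a boxed warning for the active substance. Section 6.1 of the labels says: "Gastrointestinal symptoms, increases in serum creatinine, and skin rash were dose related". Section 1.2 reports that DST-0509 was absorbed better than both marketed products. The PK part of the synopsis sets out the hypothesis that many of these inadequate responders have low exposure on their current product compared with DST-0509. Patients already at the maximal labelled dose are therefore moved to a product expected to raise exposure in many of them, without a dose reduction beyond the standard Exjade conversion. That is reasonably read as a modification of therapy in the sense of label section 5.1.

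A creatinine rise in the first two weeks on DST-0509 is first scheduled to be measured on Day 14 or Day 49. A rise without symptoms before then prompts no repeat, because no scheduled test would show it, although blood is drawn five times on Day 7 or Day 42.

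**Working it through.** The protocol states no monitoring interval in days, so there is no figure of its own to reproduce. The check is subtraction of schedule days.

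**Inputs.** Chemistry days 1, 14, 28, 36, 49 and 63 (7.11.3). First doses on Day 1 (5.4) and Day 36 (6.4.1). PK visits on Days 7 and 42 (6.3.2, 6.4.2). Visit window ±1 day, none on Day 1 (Table 6-1). For the ranges, each visit is allowed to move independently within its window.

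**1. Current first interval** (first on-drug chemistry minus first dose).
- Period 1: 14 − 1 = 13 days; with windows 13 − 1 = 12 to 15 − 1 = 14.
- Period 2: 49 − 36 = 13 days; with windows 48 − 37 = 11 to 50 − 35 = 15.

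**2. With creatinine on Days 7 and 42.**
- Period 1: 7 − 1 = 6 days; with windows 6 − 1 = 5 to 8 − 1 = 7.
- Period 2: 42 − 36 = 6 days; with windows 41 − 37 = 4 to 43 − 35 = 8.

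**3. Time from a raised value to the next scheduled one.** 14 − 7 = 7 and 49 − 42 = 7 days. With windows the shortest is 13 − 8 = 5 (48 − 43 = 5) and the longest 15 − 6 = 9 (50 − 41 = 9). The labels' one-week repeat is met at nominal days and can be overrun by up to 2 days.

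**4. What does not change.** 28 − 14 = 14 and 63 − 49 = 14 days, up to 29 − 13 = 16 and 64 − 48 = 16 with windows. Of four weekly points in a 28-day period (nominally Days 7, 14, 21 and 28 of treatment), 2 are covered now and 3 after the change.

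**5. Exposure relative to prior therapy.** Let R be the DST-0509/Jadenu AUC ratio. The documents do not give R.
- From Jadenu: 1 × R.
- From Exjade: dose ratio 28/40 = 0.70. Section 12.3 of the Jadenu label puts Jadenu AUC 36% above the suspension tablet, so 0.70 × 1.36 × R = 0.952R.
- For an assumed R of 1.1 to 1.5: 1.1 to 1.5 from Jadenu, and 0.952 × 1.1 = 1.05 to 0.952 × 1.5 = 1.43 from Exjade.
- An Exjade patient has no increase if R is at or below 1/0.952 = 1.05.

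This range is illustrative and assumes R above 1.

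**6. Number of tests.** Two per patient: 36 × 2 = 72; 30 × 2 = 60; 24 × 2 = 48.

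**The case against.** The strongest reply is that the schedule is defensible as it stands. It more than meets the boxed warnings' monthly minimum for patients not at increased renal risk, and two-weekly testing matches the labels' interval for liver tests. Section 4.2 excludes creatinine above 1.5 times ULN and urine protein/creatinine above 0.5 mg/mg. Section 4.1 requires more than 3 months of stable maximal-dose deferasirox. The weekly wording is written for Exjade and Jadenu, not for DST-0509. The absorption evidence from Study 102 comes from a "single dose, randomized, 3-period, 3-sequence crossover, oral bioavailability study of DST-0509 compared with Exjade and Jadenu in fasted healthy volunteers", whereas DST-0509 is taken here with food. The remedy does not reach weekly testing, and no dose rule in section 8.5.3 uses creatinine.

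Most of this stands, and it is why the point is a low-severity improvement. It does not remove the gain. Section 4.2 states no creatinine-clearance limit, so some patients for whom the boxed warnings ask weekly checks could enter; their number is unknown. Section 4.3 allows withdrawal for unacceptable laboratory toxicity, and section 9.1 treats a significant laboratory change as an adverse event, so an earlier value can be acted on.

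Stronger readings are tempting and are not supported:

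- A reader might infer that the schedule breaches the labels. Doing so requires counting DST-0509 as a modification of therapy, which is an inference.
- A reader might infer that an early rise cannot be detected before Day 14 or 49. It is only not scheduled to be measured; adverse events are reviewed at Visits 4 and 8, and the investigator can order tests.
- A reader might infer a known increase in exposure or in renal events. The documents give neither R nor a 28-day creatinine event rate.
- A reader might apply the argument equally to the comparator. It is weak there, because the comparator is resumed at the patient's previous dose.

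**Conclusion.** The point holds as an inexpensive safety improvement of low severity. The schedule is consistent and contains no error. In each period the first scheduled on-drug creatinine comes at 13 days (12–14 in Period 1, 11–15 in Period 2), and existing visits would allow it at 6 days (5–7 and 4–8). The longest scheduled gap stays at 14 days.

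This rests on three assumptions: that starting DST-0509 is fairly read as a modification of therapy, that exposure does rise in a meaningful share of patients, and that the Day 1 and Day 36 chemistry serves as the pre-treatment reference in each period. The value of the extra result lies in investigator judgement, including withdrawal, since no protocol dose rule turns on creatinine.

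**What to change.** Add serum creatinine only, not the full panel, at Visit 4 (Day 7) and Visit 8 (Day 42). Do so for both treatments, so that renal monitoring is the same in each period of the crossover. Update Table 6-1 and sections 6.3.2, 6.4.2 and 7.11.3. Days 21 and 56 would need new visits and are not requested.

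The cost is two single-analyte tests per patient, at most 72 for 36 patients, and no new visit. This assumes that the sample can be taken with the predose PK draw; if it cannot, one extra venepuncture per visit is needed. Sections 10.2 and 12.1 require a protocol amendment with IRB approval, with the case report forms and consent form revised if affected.

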7.12 Randomization and/or Treatment Assignment

At Visit 3 patients will be randomized and study treatment assigned.

7.13 Bristol Stool Chart

Patient's will be instructed to rate their stool using the Bristol Stool Chart in [Figure 7-1](#).

Figure 7-1: Bristol Stool Chart

7.14 Gastrointestinal AESI Diary

In addition, safety will also assess adverse events of special interest (AESI) including selected gastrointestinal AEs of diarrhea, constipation, nausea, vomiting, and abdominal pain.

8 STATISTICAL METHODS

Complete details of the statistical and PK analyses will be specified in the statistical analysis plan (SAP). The SAP will be written and finalized prior to database lock. The key aspects of those analyses are summarized below.

8.1 Sample Size Determination

The primary endpoints in this patient-pilot study are safety and tolerability with special interest in gastrointestinal AEs such as diarrhea. Evidence of DST-0509 iron chelating activity is also of special interest but is considered preliminary for this study and will not be considered in sample size estimations. If the underlying true probability of a diarrhea AE is 12% (Jadenu label 2015[2]), then there will be a 98% probability of observing at least one event in this study with a total sample size of 30 subjects. The table below presents a range of diarrhea AE rates provided from Jadenu clinical trials and the probability of observing at least 1 or 2 for our planned sample size. Given the same adverse event rate for diarrhea, there will be an 89% probability of observing at least two events in this study.

Underlying Event Rate	Probability of Observing at Least 1 Diarrhea AE		
	N=24	N=30	N=36
9%	0.90	0.94	0.97
12%	0.95	0.98	0.99
21%	>0.99	>0.99	>0.99

Underlying Event Rate	Probability of Observing at Least 2 Diarrhea Events		
	N=24	N=30	N=36
9%	0.65	0.77	0.85
12%	0.80	0.89	0.94
21%	0.97	0.99	>0.99

It is expected that most reasonably common AEs will be observed in this small study and will provide information for future studies.

8.2 Analysis Populations

Four analysis populations are defined for this study as follows:

- **Safety Population:** All patients who received the planned study medication. The Safety Population will be used to assess safety and tolerability. Patients in the Safety Population will be analyzed with actual treatment.

- Intent-to-Treat (ITT) Population: The ITT population comprises all patients who received at least 1 dose of study medication and had at least 1 evaluable efficacy measurement after the first dose of DST-0509. Patients in the ITT population will be analyzed as randomized to treatment sequence.
- Per Protocol (PP) Population: The PP population comprises all randomized patients who completed the study according to all protocol requirements.
- PK Population: All patients who receive planned study medication and have sufficient post Baseline plasma samples obtained and assayed for drug concentration levels to allow for computation of PK parameters will be included in the PK Population. Patients will be included in the PK Population after review of the plasma concentration data. The rationale for inclusion or exclusion in the PK Population will be documented and listed.

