3.1 Overall Study Design

This is a multi-center, open-label, two-period cross-over, patient-pilot study comparing DST-0509 to Exjade or Jadenu administered orally once daily (QD) for 28-days in each period, with a 7-day washout before study entry and between treatment periods (see Table 6-1). Patients will be randomized to one of two treatment sequences: DST-0509→Exjade/Jadenu or Exjade/Jadenu→DST-0509 (with subjects who were taking Exjade prior to study start receiving Exjade and those taking Jadenu at study start receiving Jadenu). This study is designed to assess the safety, tolerability, evidence of iron chelating activity, and PK profile of DST-0509 compared to Jadenu or Exjade in inadequately responding patients. Inadequate response to standard chelation therapy is defined from the medical literature [6,7].

Up to 36 patients will be randomized 1:1 into one of two treatment sequences (study arms), of which up to 100% may be on Jadenu or Exjade at study entry, or a mix of the two. The planned randomization will assign up to 18 patients in each of two sequences: Sequence A: DST-0509 crossed to Exjade or Jadenu; Sequence B: Jadenu or Exjade crossed to DST-0509. The comparator treatment will be the patient's current chelation treatment. At the end of the study, patients previously on Jadenu or Exjade will revert to receiving their pre-study medication and dose following a 7-day washout period. A sufficient number of patients will be enrolled so there will be no need to replace study drop-outs. Study duration is approximately 14 weeks for each patient. A Study Flow Diagram is presented after this Synopsis (see Figure 3-1).

Figure 3-1: Study Flow Diagram

Treatment A (28 days) = DST-0509
Treatment B (28 days) = Jadenu/Exjade¹

*Up to 36 patients are planned.

- Subjects taking Exjade prior to study start will receive Exjade (treatment B) in the assigned Period 1 or cross-over Period 2. Those patients taking Jadenu prior to study start will receive Jadenu (treatment B) in the assigned Period 1 or cross-over Period 2. Dosing will be at equivalent (mg for mg) doses of DST-0509 for Jadenu. If crossing over from Exjade to DST-0509, or vice versa, the dose will be scaled to 28 mg/40 mg (DST-0509/Exjade).
- For all patients entering the trial, a 7-day washout is required.

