4 SELECTION AND WITHDRAWAL OF PATIENTS

The study will enroll up to 36 patients and no study drop-outs will be replaced. Patients who have provided written informed consent and an authorization for disclosure of protected health information must meet all of the following criteria to qualify for entry into the study.

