6.6 Early Termination Procedures

The term "Early Termination" refers to a patient's non-completion of a study whether by his or her own choice or the Investigator's decision or due to discontinuation of the study by DisperSol.

In the absence of a medical contraindication or significant protocol violation, every effort will be made by the Investigator to keep the patient in the study. Should the patient decide to

withdraw, an attempt will be made to conduct an early termination visit, which will include all procedures normally done at Visit 10 (Day 63) and, the patient should be requested to undergo a 7-day washout and have a phone call to confirm as in the Follow-up (Day 70) procedures.

The primary reason for a patient withdrawing prematurely should be selected from the following categories:

Adverse Event or Serious Adverse Event - events that are associated with discontinuation.

Noncompliance with protocol - The patient failed to adhere to the protocol requirements. The deviation necessitated premature termination from the study.

Pregnancy - The patient became pregnant after enrolling the study. Pregnant patients are withdrawn from the study as soon as the Principal Investigator is aware of the condition.

Laboratory Abnormality - Laboratory abnormality that does not meet the definition of an AE.

Withdrawal of Consent - The patient desires to withdraw from further participation in the study in the absence of an adverse event or a medical need to withdraw.

Lost to Follow-up - The patient did not return for follow-up visit(s) following dispensing of test drug.

Other - causes of premature termination from the study other than the above, such as theft or loss of investigational product, termination of study by DisperSol, etc.

The Investigator should notify Accelovance, Inc. promptly when a patient is withdrawn, or if the study is stopped at his/her site by the IRB or if the Investigator elects to stop the study.

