7.10 Ferritin Monitoring

Ferritin (mcg/L) will be assessed in serum or plasma (at Screening, Eligibility and on Days 1, 28, 36 and 63) with enzyme-linked immunosorbent assays (ELISA) by routine laboratory methods.

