8.4 Randomization

This study will investigate 2 treatment groups:

Group (Treatment)	Treatment Assignment
1 (A/B)	DST-0509 / Jadenu (Exjade)
2 (B/A)	Jadenu (Exjade) / DST-0509

A computer-generated randomization scheme will be used to obtain a balanced allocation to each treatment group.

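### The ITT definition requires a measurement after DST-0509, so comparator-first patients who leave before Period 2 are always excluded, while DST-0509-first patients leaving at the same point can stay in

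*Protocol*

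**What the plan says.** Section 8.2 of the protocol sets two conditions for ITT membership. The patient must have taken at least one dose of study medication, and must have "had at least 1 evaluable efficacy measurement after the first dose of DST-0509". The synopsis (Statistical Analyses) repeats the definition unchanged, so it is not a slip in one place. Section 8.2 adds: "Patients in the ITT population will be analyzed as randomized to treatment sequence".

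Other sections fix when DST-0509 can be taken and when ferritin is measured:

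- Section 8.4 defines the second group as "Jadenu (Exjade) / DST-0509", so its patients first take DST-0509 in Period 2, which starts at Visit 7 (Day 36 ±1; Section 6.4.1).
- Section 3.1: "The planned randomization will assign up to 18 patients in each of two sequences".
- Section 7.10 schedules ferritin "at Screening, Eligibility and on Days 1, 28, 36 and 63".
- Section 6.4.4 includes ferritin at Visit 10/Early Termination, and Section 6.6 says that for a withdrawing patient an attempt is made to hold that visit.
- Section 4: "no study drop-outs will be replaced". Section 8.3 rules out imputation.

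**The concern.** Naming DST-0509 in the second condition makes the same rule act differently in the two sequences. In the DST-0509-first sequence it means a ferritin after Day 1. In the comparator-first sequence it means completing the comparator period and the washout, starting DST-0509, and then having a ferritin. In that sequence alone, membership depends on an event after randomisation that the comparator treatment may itself influence.

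The set is then analysed by randomised sequence, as if the sequences still had the composition that randomisation gave them. At stake is the comparison of iron-chelating activity with Jadenu or Exjade. This is part of the primary objective (Section 2.1), and the synopsis names change in ferritin within each treatment period as its main efficacy variable. Ferritin values observed on the comparator would be discarded, and the patients who remain would have been selected differently by sequence.

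**Working it through.** **The plan's own figures.** The only numerical planning result is the probability of seeing diarrhoea events (Section 8.1). At a 12% rate and N = 30, the binomial gives P(≥1) = 1 − 0.88^30 = 0.978 and P(≥2) = 0.890, matching the stated 98% and 89%. All 18 cells of the two tables reproduce at the stated rounding. The ITT definition does not enter these figures, so they neither depend on this point nor settle it.

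**Who qualifies under the rule as written**

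| Patient leaves | DST-0509 first | Comparator first |
|---|---|---|
| Period 1, before Day 28 | In, if an early-termination ferritin is obtained | Out, whatever was measured |
| Washout, after the Day 28 visit | In, with the Day 28 ferritin | Out, despite a Day 28 ferritin on the comparator |
| Period 2, before Day 63 | In, with the Day 28 ferritin | In only if an early-termination ferritin is obtained |

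The last row takes the Day 36 ferritin to be the pre-dose Period 2 baseline.

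**Inputs.** n = 18 per sequence (Section 3.1, the planned maximum). The protocol gives no drop-out rate, so d, the loss per period, is assumed at 5-20% and equal in both periods and sequences. Washout losses count with Period 1. The share of leavers with a ferritin after their last treatment began, e, is also assumed (0, 0.5 or 1).

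**Formulas**

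- Kept, DST-0509 first: A = n[(1 − d) + d·e]
- Kept, comparator first: B = n(1 − d)[(1 − d) + d·e]
- Gap: A − B = n·d·[(1 − d) + d·e]

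**Results (expected patients kept, A / B, gap)**

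| d | e = 1 | e = 0.5 | e = 0 |
|---|---|---|---|
| 5% | 18.00 / 17.10, gap 0.90 | 17.55 / 16.67, gap 0.88 | 17.10 / 16.24, gap 0.86 |
| 10% | 18.00 / 16.20, gap 1.80 | 17.10 / 15.39, gap 1.71 | 16.20 / 14.58, gap 1.62 |
| 15% | 18.00 / 15.30, gap 2.70 | 16.65 / 14.15, gap 2.50 | 15.30 / 13.00, gap 2.30 |
| 20% | 18.00 / 14.40, gap 3.60 | 16.20 / 12.96, gap 3.24 | 14.40 / 11.52, gap 2.88 |

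The comparator-first sequence keeps fewer patients in every cell, so the asymmetry does not depend on how well early-termination ferritin is captured.

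**Removed by definition.** The expected number of comparator-first patients who leave before Period 2 is 18d = 0.9, 1.8, 2.7 and 3.6 at 5, 10, 15 and 20%. That is 2.5% to 10% of 36 patients. The chance that at least one is removed is 1 − (1 − d)^18 = 0.60, 0.85, 0.95 and 0.98.

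**With the condition tied to any study medication.** Both sequences keep the A figures under equal drop-out, and the gap is zero.

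**The case against.** Several points on the other side stand and limit what can be claimed.

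- **Efficacy is preliminary.** Section 8.1 excludes chelating activity from the sample-size reasoning, and Section 8.5 calls the efficacy endpoint analyses exploratory. Safety has its own population. No confirmatory claim rests on the ITT set.
- **The link to the ferritin model is inferred.** Section 8.5.2 does not say which population the MMRM uses. ITT is the natural reading but is not stated. A patient with a comparator Period 1 only gives no within-patient contrast, so the information lost to the treatment comparison is smaller than the head count suggests.
- **High drop-out on the comparator may be unlikely.** Those patients continue their own drug after more than 3 months of stable dosing and a compliance check (Section 4.1). This favours the lower end of the assumed range.
- **Retention in the DST-0509-first sequence is conditional.** Section 6.6 promises only an attempt at the early-termination visit, so it cannot be said that this sequence loses nobody.

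A reader might also infer two stronger conclusions that the protocol does not support.

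- **That the bias has a known direction.** The withdrawal reasons in Section 6.6 are adverse events, noncompliance, consent and the like, not ferritin outcome. Removing poor comparator responders could even flatter the comparator.
- **That the Safety Population, "All patients who received the planned study medication", also drops early stoppers and so under-counts adverse events.** Section 8.2 speaks of completion only for the per-protocol set, and says safety patients are analysed by actual treatment. Section 8.5.3 plans a table of adverse events associated with discontinuation, which presumes that early stoppers are in the set.

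None of this removes the asymmetry in the ITT rule, and no other section offsets it.

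**Conclusion.** The point holds for the ITT definition alone. As written, the rule admits patients differently by randomised sequence, in a set that is then analysed by that sequence. This is a stated rule that is wrong, not a detail left to the SAP.

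The size is modest: about 1 to 4 comparator-first patients removed by definition out of 18. This rests on an assumed 5-20% Period 1 loss and full enrolment. With 12 per sequence, the smallest size in the protocol's tables, it would be 0.6 to 2.4 (12 × 0.05 to 12 × 0.20). The consequence is discarded comparator ferritin data and a possible bias, of unknown direction and size, in a comparison the protocol calls preliminary. The definition should be corrected before analysis, but it does not undermine the trial's safety objective or its sample-size figures.

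**What to change.** In Section 8.2 and in the synopsis, change the second ITT condition to at least one evaluable efficacy measurement after the first dose of any study medication (DST-0509, Jadenu or Exjade). Keep the analysis by randomised sequence, and carry the same wording into the SAP, which was not available here.

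The revised set still requires dosing and a post-dose ferritin, so it remains a modified ITT set. What the change removes is the difference in the entry rule between sequences. The cost is one phrase in two places of the protocol, with no new visits or data. It should be made before the data are analysed, because redefining a population afterwards would look post hoc.
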